- Participants must have been in treatment with an SSRI for at least 8 weeks, the last 4 of which were at a dosage of ≥ 20 mg per day of fluoxetine or its equivalent, e.g. 20 mg per day of paroxetine, 20 mg citalopram, 10 mg escitalopram, or 100 mg sertraline. If the participant attempted, but could not tolerate, a dose comparable to 20 mg fluoxetine, they will be considered eligible. (This definition of "Adolescent SSRI Resistant Depression" is modified from the NIH-sponsored, \$17 million TORDIA Randomized Controlled Trial [<http://clinicaltrials.gov/ct2/show/NCT00018902>] [128].

Exclusion Criteria:

- Unstable co-morbid medical, neurological, or psychiatric disorder.
- Current DSM-IV criteria for substance abuse or dependence (excepting nicotine/cigarettes).
- Clinically significant suicidal or homicidal risk.
- Pre-existing renal disease.

- Proteinuria on baseline urinalysis testing.
- Pregnancy or breastfeeding.
- Sexually active and unwilling to practice contraception during the study.
- Contraindication to magnetic resonance imaging (e.g. ferromagnetic implant or claustrophobia)
- History of hypersensitivity to creatine.
- History of a previous failed therapeutic trial of creatine.
- Participants may be outpatients or inpatients, but incarcerated persons will be excluded because this study is not approved for "Research Involving Prisoners."
- More than 2 suicide attempts prior to the screening visit
- Participants who made a suicide attempt within 6 months prior to the screening visit

Study Withdrawal Criteria:

- Withdrawal of parental permission, participant informed consent, or participant assent.
- Onset of a psychotic disorder or bipolar disorder.
- Intolerable or clinically significant side effects to creatine.
- Worsening depression, as demonstrated by an increase in CDRS-R or MADRS score $>25\%$ from baseline.
- Positive pregnancy test.
- A significant change to the participant's medication or psychotherapy treatment from the regimen reported at their baseline/screening visit (e.g. the SSRI is discontinued).
- Incarceration, as the study is not approved to conduct "Research Involving Prisoners."
- If a clinically significant intracranial lesion is found by the Radiologist on a participant's baseline brain scan, they will be withdrawn from the study and referred for appropriate medical care.

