- "*The study involves adding a new investigational therapy to an established effective therapy*" (#4): The FDA has approved the SSRI medicines fluoxetine and escitalopram to treat adolescent depression. The guidelines of the American Academy of Pediatrics, and the American Academy of Child & Adolescent Psychiatry advocate cautious use of SSRIs to treat adolescents with MDD. This is an **augmentation** study, meaning this protocol does not remove an established treatment from any participant. All participants will **not** have a "washout period." All participants must continue on an adequate dose of a prescription SSRI antidepressant throughout the time they are enrolled in the study.
 - This is similar to the Placebo Justification listed on the ERICA website, which says: "Any placebo use in this trial is in addition to usual and standard therapy." The proposed study conforms to this criterion, as only participants whose depression has proven resistant to standard antidepressant treatment are eligible. Furthermore, participants in the placebo group will **not** discontinue their SSRI prescription during the study. On the contrary, they must **continue** the usual and standard therapy throughout their participation in the trial.
- "*Participants have determined that the response to the established effective therapies for their condition is unsatisfactory to them*" (#5): the proposed study will only enroll adolescents who have had an adequate trial of a standard-of-care SSRI antidepressant treatment, and who continue to meet diagnostic criteria for major depression with at least moderate residual symptoms. Persons who have never taken an SSRI antidepressant, or who consider their response to SSRI(s) to be satisfactory, will be excluded from participation in this study.

Participants will undergo neuroimaging at baseline, prior to administration of investigational drug. The neuroimaging will then be repeated following 8 weeks of study drug. If the study treatment is tolerated well, after the initial 8 weeks, open-label continuation treatment with

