creatine monohydrate 10g/day will be offered for 6 months. The open-label extension offers participants initially randomized to placebo an opportunity for a 6-month therapeutic trial of adjunctive creatine at no cost, with monitoring by the research team and 24/7 cellphone access to a board-certified child psychiatrist. Participants who elect to take 10g/day of creatine will be scheduled for monthly visits over the course of 6 months. At the sixth visit, repeat labs will be obtained. Additionally, per [name] discretion, supplementary labs may be obtained throughout the open-label follow-up phase.

STUDY PROCEDURES:

All procedures performed by study personnel are research-related. None of the study activities will be considered standard of care. There will be no cost to study subjects for their participation. Participants will be compensated for their time and travel. **Table 1** outlines the schedule of study procedures.

Consent will be obtained before any study procedures are initiated. Potential participants will be informed of the study and offered a consent form to review. They will be encouraged to discuss study participation with their relatives. If a potential participants expresses interest in study participation, the informed consent process will be conducted. After the informed consent process, individuals will be offered time to consider study participation and to ask questions. Subjects and parents/guardians will have the opportunity to discuss the study with a study team member in a setting free of coercion. The language of the informed consent form is written at a level easily understood by the subject and any questions asked by the subject will be answered honestly and free of bias. A specific meeting time will be set up between a study team member and the participant where the entire informed consent document will be carefully explained in its entirety. The length of the meeting will be designed so there is the necessary amount of time for all questions to be answered.

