Randomization of participants to the two treatment conditions will take place according to a randomization list generated prior to the start of recruitment, by an individual ([name]) who will have no contact with participants or with study drug. Thirty-three participants (50%) will be randomized to placebo. The study will be conducted as a double-blind trial, with neither participants nor research staff aware of participant assignment. Except in cases of medical emergency, the double-blind will not be "broken" until recruitment is closed and the final participant has completed 8 weeks of treatment with investigational drug. There is no "washout period" for any participant in this study, and participants randomized to placebo will continue treatment with a prescription SSRI antidepressant throughout their time in the study.

If during the MRI/MRS scans we unexpectedly discover something that warrants further inspection, we will refer the participant to her primary care provider for follow-up, along with the MRI/MRS report that shows the findings. Any costs related to following up on unexpected findings will be the responsibility of her and/or her insurance provider.

Participants will be compensated for their participation. The overall expected amount of compensation per MDD participant will be 245 dollars and participants will be paid at each visit. Payment of compensation will vary from visit to visit depending on the length of time needed for that session. Sessions that are scheduled to take longer (e.g., initial screenings, MRI's, and end of study visits) will be compensated accordingly. In order to avoid study participation costing participants money due to travel expenses, participants traveling more than 100 miles round trip per study visit will be given an additional \$50 at the week 10 visit, making their total

compensation for the study \$295. Participants that are screened but not eligible to enroll in the study will be compensated \$25.

HC participants will be paid \$25 for the screening visit and \$50 for the scan visit, totaling \$75.

Table 1: Schedule of Procedures for Major Depression (MDD) & Healthy Control (HC) Participants

Study Week #	- 1	0	1	2	3	4	6	8	10
Parent / Guardian Consent and Participant Assent OR Participant Consent	MDD HC								
Medical History & Physical Exam	MDD								
Electrocardiogram, Phlebotomy for Serum Labs (CBC & CMP), Urinalysis*†	MDD							MDD	
Urine HCG Test & Drug Screen*	MDD HC	MDD HC						MDD	

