Randomization		MDD							
Dispense Study Medication**		MDD	MDD	MDD	MDD	MDD	MDD	MDD	
KSADS-PL (< 18 years old) or SCID (> 18 years old)	MDD HC								
CDRS-R, CGI, C-SSRS, MADRS, Safety Plan	MDD HC	MDD HC	MDD						
DAS	MDD							MDD	
Vital Signs, Concomitant Meds, Adverse Events	MDD HC	MDD HC	MDD						
3-Tesla MRI / ³¹ P-MRSI Brain Scan		MDD HC						MDD	

CBC = complete blood count

CMP = comprehensive metabolic panel

CDRS-R = Children's Depression Rating Scale-Revised

CGI = Clinical Global Impression Scale

C-SSRS = Columbia-Suicide Severity Scale

KSADS-PL = Schedule for Affective Disorders and Schizophrenia for School-Age Children-Present and Lifetime Version

SCID = Structured Clinical Interview for DSM-IV Disorders

MADRS = Montgomery-Asberg Depression Rating Scale

DAS= Dysfunctional Attitude Scale

MRI = Magnetic Resonance Imaging

³¹P-MRSI = 31-Phosphorus Magnetic Resonance Spectroscopy Imaging

*May be collected at Study Week #0 only if time does not permit for the collection of these during Study Week #-1.

**Participants will not begin taking study medication until serum lab and urinalysis results have been reviewed by [name].

† Per [name] discretion, additional lab tests may be ordered throughout the open-label follow-up phase.

Table 2: Schedule of 6-Month Follow-Up Procedures for MDD Participants

Month #	1	2	3	4	5	6
Phlebotomy for Serum Labs (CBC & CMP) and Urinalysis †						x
Dispense Study Medication	x	x	x	x	x	x
CDRS-R, CGI, C-SSRS, MADRS, Safety Plan	x	x	x	x	x	x
DAS						x
Vital Signs, Concomitant Meds, Adverse Events*	x	x	x	x	x	x

CBC = complete blood count
 CMP = comprehensive metabolic panel
 CDRS-R = Children's Depression Rating Scale-Revised
 CGI = Clinical Global Impression Scale
 C-SSRS = Columbia-Suicide Severity Scale
 MADRS = Montgomery-Asberg Depression Rating Scale
 DAS= Dysfunctional Attitude Scale

*Adverse events will not be evaluated after the follow-up portion of the study

† Per [name] discretion, additional lab tests may be ordered

RISKS AND BENEFITS TO STUDY PARTICIPANTS

- During the intake and assessment interview, participants may become emotionally upset when asked about their psychiatric history including suicide attempts, or physical and sexual abuse.
- There is a 50% chance that the participant will be assigned to placebo, in which they will not receive creatine.
- Participants may experience discomfort or swelling when blood is drawn for laboratory tests. Rarely, infection can result from blood draws.

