1.2 Monitoring of Safety Data by the DSMB and the Research Team

Range of Safety Reporting by the study team to the DSMB. The study team will provide the following information to the DSMB for its review on an annual basis: Serious Adverse Events (SAEs), Unanticipated Adverse Events (UAEs), Adverse Events (AEs), Unanticipated Problems (UPs), study retention rates, reasons for early study withdrawal, and abnormal laboratory values that are determined to be related to study participation. The DSMB will have access to any additional data it deems necessary to fulfill its mission. The study team will respond promptly to any DSMB data requests.

Anticipated Adverse Events

Anticipated Adverse Events for this study include the following:

- Emotional upset due to questions during the assessment about participants’ psychiatric and social histories (including current suicidal ideation, history of suicide attempts, and history of physical or sexual abuse);
- Pain, swelling or infection due to phlebotomy for blood laboratory testing;

- Nausea, diarrhea, vomiting, abdominal gas or bloating, appetite changes, headache, edema or weight gain associated with administration of the investigational drug creatine;
- Injury due to mobilization of metallic objects inadvertently brought or worn by the participant into the MRI scanner. (The MRI technicians will make every effort to avoid this by reminding the participant and their parent or guardian to take the appropriate precautions prior to entering the scanning suite. An MRI safety questionnaire must be completed by participants immediately prior to each scanning session.);
- Claustrophobia (fear of being in small spaces), dizziness, headache, metallic taste in the mouth, double vision, visions of flashing lights, or tingling in the back during the MRI scans. All of these events are rare, temporary and not medically dangerous.
- Worsening depression, suicidal ideation, and/or suicide attempts as part of the illness of MDD.

The effects of creatine and MRI scans on a developing fetus are unknown, so participants will undergo pregnancy testing, and will be withdrawn from the study if they have a positive pregnancy test. Sexually active persons unwilling to practice contraception during the study will be excluded from participation.

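### The pregnancy test-and-withdraw safeguard is stated without a phase limit, but no test is scheduled in the six-month open-label creatine extension

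*Combined protocol and SAP*

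**What the plan says.** The reason and the rule stand together in section 1.2 (Monitoring of Safety Data by the DSMB and the Research Team). The reason is "The effects of creatine and MRI scans on a developing fetus are unknown", and the rule that follows is that "participants will undergo pregnancy testing, and will be withdrawn from the study if they have a positive pregnancy test". Under Participant Selection Criteria, the study withdrawal criteria for MDD subjects list "Positive pregnancy test" with no reference to a phase.

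The Design section describes two periods on study drug. The blinded period lasts eight weeks: "The neuroimaging will then be repeated following 8 weeks of study drug". After that, if treatment has been well tolerated, "creatine monohydrate 10g/day will be offered for 6 months". On visits in the extension it says "Participants who elect to take 10g/day of creatine will be scheduled for monthly visits over the course of 6 months". It also allows supplementary laboratory tests by discretion during the extension, and names neither a test nor a time.

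Table 1 has a row "Urine HCG Test & Drug Screen", marked for MDD participants at weeks -1, 0 and 8. A footnote lets the week -1 sample be taken at week 0 if time is short. Table 2 is titled "Schedule of 6-Month Follow-Up Procedures for MDD Participants". Its rows are serum laboratory tests with urinalysis (month 6 only), dispensing (months 1 to 6), rating scales with the safety plan, the DAS (month 6), and vital signs with concomitant medications and adverse events. It has no HCG row.

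**The concern.** The safety text ties pregnancy testing to the drug as well as to the scans. The scans end at week 8 and the drug does not. A reader of section 1.2, such as an IRB or DSMB member, could reasonably take it that testing continues for as long as creatine is given. The schedule that site staff will follow does not provide for that.

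Participants are females aged 12 to 21, and the protocol itself calls the fetal effects unknown. If the schedules are followed as written, a participant who takes the full extension gets six monthly supplies of creatine with no planned test after week 8. An unrecognized pregnancy would then come to light only through self-report or a discretionary test.

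**Working it through.** The plan gives no figure to reproduce here. The check compares the two schedules and then works out how much drug time lies in the extension.

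**1. Does the rule reach the extension?** Neither section 1.2 nor the MDD withdrawal list limits it to the blinded phase. A footnote to Table 2 describes the follow-up as a portion of the study, so withdrawal from the study is meaningful there. The stated reason also applies. Healthy comparison subjects, who take no creatine, are excluded if pregnant because of the scans alone. For MDD participants the drug is named as a reason in its own right.

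**2. Which tests are planned?**

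| Period | Schedule | HCG tests planned (MDD) | Creatine or placebo dispensed |
|---|---|---|---|
| Screening and blinded phase | Table 1 | Weeks -1, 0 and 8 | Yes |
| Open-label extension | Table 2 | None in 6 monthly visits | Yes, at all 6 visits |

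The only laboratory row in Table 2 is the serum panel and urinalysis at month 6, and it does not name HCG. The footnote on additional tests is attached to the serum and urinalysis rows. In Table 1 it is not attached to the HCG row.

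**3. What share of drug time has no scheduled test after entry?** Inputs: 8 weeks blinded and 6 months open-label (Design section).

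Share = open-label weeks / (blinded weeks + open-label weeks)

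- 6 months taken as about 26 weeks: 26 / (8 + 26) = 26/34 = 0.76
- 6 months taken as 24 weeks: 24 / (8 + 24) = 24/32 = 0.75

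For a participant first randomized to placebo, creatine exposure in the blinded phase is zero, so the share of creatine time is 26/26 = 100%.

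**4. How does this compare with the blinded phase?** The longest planned gap between tests in Table 1 is 8 weeks (week 0 to week 8). The extension runs for 24 to 26 weeks with no test, which is 24/8 = 3.0 to 26/8 = 3.25 times as long.

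**5. How many participants?** The ceiling is the 66 randomized. With the 10% attrition assumed in the sample-size section, 66 × 0.90 = 59.4, so about 60 would reach week 8, roughly 30 of them from the placebo arm. The extension is optional and the documents give no expected uptake, so the number affected lies between 0 and about 60 on the plan's own attrition figure.

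**The case against.** The strongest reply is that this is a gap and not a contradiction. Section 1.2 promises testing without a frequency, Table 1 delivers tests, and nothing in Table 2 denies that a positive test would lead to withdrawal. The protocol has other withdrawal criteria that depend on an event and have no repeated scheduled test: onset of psychotic or bipolar disorder is one, and the diagnostic interview is planned only at week -1. How often to test is partly a matter of judgment, and Table 1 itself has no test between weeks 0 and 8.

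Much of this stands. A withdrawal criterion can exist without a dedicated test, and no particular frequency follows from the text. But the pregnancy provision differs from the psychiatric one, because section 1.2 commits to testing as well as to withdrawal and bases that commitment partly on the drug. The text does not say whether the commitment covers the longer part of dosing.

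A reader might go further and infer that the safeguard cannot work in the extension, or that protection ends at week 8. The documents do not support either reading:

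- The contraception requirement applies for the whole study.
- The withdrawal criterion has no end date.
- Monthly visits record adverse events and concomitant medications, so a pregnancy can be reported.
- Discretionary laboratory tests are allowed.
- The week 8 test falls at the end of the blinded phase, before the month 1 visit.

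What stops at week 8 is scheduled testing only. None of the continuing measures is a planned test: contraception does not detect pregnancy, and the discretionary provision names no test and no timing.

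**Conclusion.** The point holds as a mismatch between the safety text and the open-label schedule. Testing and withdrawal are stated without a phase limit and are justified partly by the drug, yet no pregnancy test is scheduled after week 8. For a participant who completes the extension, that leaves 75% to 76% of study-drug time, and all creatine time for those first on placebo, without a planned test.

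The percentages assume that the extension follows the blinded phase directly and is taken in full. They do not describe participants who decline it or leave early. The consent pages are not part of the public document, so nothing can be said about what participants are told. The primary hypothesis concerns metabolite change over eight weeks and is untouched; this is a matter of participant safety and protocol consistency. It should be settled before participants enter the extension.

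**What to change.** Reconcile section 1.2 and the MDD withdrawal criteria with Table 2. Either show the test-and-withdraw safeguard in the open-label schedule, or state expressly that scheduled testing does not cover that phase. The consent documents should be checked against whichever is chosen. The choice, and any timing, belong to the investigators and the IRB.

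The cost is a small amendment, which the protocol says must go to the IRB and the FDA. If testing is scheduled, there is a minor added burden for participants and staff at visits that already take place. Sample size, randomization and the primary analysis stay as they are.

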1.3 Monitoring of Data Quality by the DSMB

The DSMB will receive annual reports prepared by the principal investigator and the study coordinator on data quality and completeness. This will include an overview of recruitment and retention, a summary report describing participants' adherence to the protocol's procedures and investigational drug, and a summary of the completeness and quality of the data elements needed to characterize the participants and their primary and secondary outcomes. These reports will be used by the DSMB to evaluate the adequacy of the research team's data capture and management to support a scientifically valid analysis at the study's conclusion. The DSMB will make recommendations to improve data management as needed. After reviewing the report, the DSMB will send a letter to the principal investigator recommending that the study continue, or that the study be halted due to safety concerns. All DSMB letters will be submitted to the IRB.

METHODS, DATA ANALYSIS AND INTERPRETATION:

1. Neuroimaging Protocol

i. Magnetic Resonance Imaging (Siemens Trio 3T MRI system)

MRI scans will be conducted twice: at the baseline visit, and following 8 weeks of treatment with study drug. The 3.0 Tesla Siemens whole-body clinical scanner (Siemens Medical Solutions, Erlangen, Germany) located within the University Neuropsychiatric Institute (UNI) will be used to acquire this data. Participants will first undergo a routine anatomic MRI protocol, which includes MRI images acquired in the axial and coronal planes. Specifically, the anatomic scan protocol consists of a T1 weighted structural scan (MPRAGE), and double-echo T2 weighted scan, and a Fluid Attenuated Inversion Recovery scan (FLAIR). The purposes of the MR anatomic screening session include screening subjects for gross structural abnormalities and acquiring images for use in brain cortical thickness measurements. Anatomic MRI examinations will be performed with a quadrature radio-frequency coil. After localization, anatomical imaging will be obtained using a T1-weighted, sagittal oriented 3D-Magnetization Prepared Rapid Gradient Echo (MPRAGE) sequence (TR/TE/TI 2100/3.97/1100 ms, matrix 256x256, FOV 256x256 mm, flip angle 12 degree, slice thickness 1.5 mm, slab 192 mm, bandwidth 190 Hz/pixel). Axial proton-density and T2 weighted images will be acquired to screen for brain structural abnormalities using 2D Double echo T2 weighted turbo spin echo (TSE) sequence (TR 7110 ms, TE 28/84 ms, FOV 240x210, slice thickness 3 mm, flip 150°, bandwidth 179 Hz/pixel). FLAIR sequence (TR/TE/TI 8000/90/2500 ms, slice thickness 5 mm, FOV 240x168, voxel size 0.8x0.6x5.0 mm, bandwidth 200 Hz/pixel, turbo factor 13) will be used to detect juxtacortical-cortical lesions. All anatomic MRI images will be read by a board-certified Radiologist to screen for structural abnormalities.

ii. Measurement of *In-Vivo* Brain Chemistry Using Phosphorus-31 Magnetic Resonance Spectroscopy (^{31}P -MRS)

a. Phosphorus MRS

Phosphorus spectroscopy data will be acquired on the same Siemens 3T system. We aim to keep the duration of each MRSI examination at or under 25 minutes. A 3D-MRSI sequence with elliptically weighted phase-encoding will be used to collect ^{31}P -MRSI data to minimize T2 signal decay. Acquisition parameters will be: data matrix size 16x16x8; TR 2000 ms; tip-angle 90 degree for hard RF pulse; Rx bandwidth ± 1 kHz; complex-points 1024; readout duration 256 ms; pre-acquisition delay 0.3ms; FOV 240x240 mm²; 16 NEX.

iii. Spectral Analysis of ^{31}P -MRS Data

Spectroscopy will be analyzed using Liner Combination of Model Spectra (LCModel) [130], which analyzes an *in vivo* spectrum as a linear combination of model *in vitro* spectra from individual metabolite solutions. This model is fully automatic and user independent. A nearly

model-free constrained regularization method is used for convolution and baseline. For quantification, absolute metabolite concentrations (institutional units) will be estimated using the unsuppressed water signal as an internal concentration reference. Also, total creatine levels will be used as a denominator for calculating the relative concentration for the comparison with previous reports. The standard Siemens libraries of model metabolite spectra provided with LCModel will be used in the basis set. The metabolites from the basis set will include alanine, aspartate, creatine, gamma-amino butyric acid, glucose, glutamine, glutamate, glycerophosphocholine, glutathione, myo-inositol, scyllo-inositol, lactate, N-acetylaspartate, N-acetylaspartylglutamate, phosphocholine, phosphocreatine, phosphoethanolamine, scyllo-inositol, and taurine. For the reliability of detection, the Cramer-Rao lower bounds (CRLB) will be determined: the acceptable upper limit of estimated standard deviations will be set at 20% [131].

Post processing of ^{31}P -MRS data will be conducted using jMRUI software (jMRUI v. 4.0, European Community) with the AMARES algorithm (Advanced Method for Accurate, Robust and Efficient Spectral fitting of MRS data with use of prior knowledge). Before fitting the FID (Free-induction-decay) data, a Hamming filter will be applied to reduce signal contamination from neighboring voxels, with apodization of 10 Hz line broadening. Fourier transformation, frequency shifts correction, and zero-order/first order phase correction as well as baseline correction will be applied. The structural image-processing tool FSL (FMRIB Software Library, Release 4.1, The University of Oxford) will be used to account for gray matter, white matter, and cerebrospinal fluid (CSF), in order to correct the partial volume effects on metabolite concentrations. The MRS grid will be positioned over the images in an identical fashion between baseline and treatment scans for each participant. The peak area for each ^{31}P -MRS metabolite will be calculated as a percentage of the total phosphorus signal.

Statistical Analyses

We hypothesize that at baseline, CDRS-R scores are negatively correlated with cerebral PCr in female adolescents with SSRI-resistant MDD. We also hypothesize that for participants whose MDD responds to creatine, change CDRS-R score will be inversely correlated with change in brain beta-NTP levels (i.e. participants who have a significant decrease in their CDRS-R score will show an increase in beta-NTP).

Both intent-to-treat (ITT; encompasses all participants who receive >1 dose of study drug) and protocol completer analyses will be performed. A participant completing 8 weeks of treatment and both ^{31}P -MRS scans will be considered a "completer." Data will be expressed as mean + standard deviation (SD). Group differences in demographic variables involving continuous data will be calculated using one-way analysis of variance. Between-group comparisons involving categorical variables will be assessed using Fisher's exact test for n x k contingency tables. A linear mixed model (LMM) will be used to account for the association between measurements (baseline and post-treatment) for each individual for the repeated measures analysis. Exploratory data analysis using non-parametric statistical tests (e.g., Wilcoxon Rank-Sum test and the Mann-Whitney U-test) will also be performed. Statistical significance will be defined at the two-tailed, 0.05 level. Stata 11 (StataCorp LP, College Station, TX) and SAS 9.2 (SAS Institute, Cary, NC) software will be used for statistical calculations. Confidence intervals for all estimated parameters will be constructed using a 95% level.

Power Analysis and Sample Size Calculations: Calculations are based on the open-label female adolescent SSRI-resistant MDD creatine data obtained at our site, and our adult creatine studies. All power calculations are two-tailed with an alpha level of 0.05, and were performed in the specialized software PASS (NCSS, Kaysville, UT). The minimum required sample size

satisfying our hypothesis is 30 creatine-treated, 30 placebo-treated, and 30 age-matched healthy controls. Assuming a 10% attrition rate for MDD subjects and a 30% attrition rate for healthy controls, we propose to enroll a total of 66 female adolescents with SSRI-resistant MDD and 40 healthy controls. The central hypothesis and power analysis for the R33 clinical trial are described below.

The hypothesis that PCr and beta-NTP levels measured with 31P-MRS will show significant change associated with 8 weeks of 10g daily creatine compared with placebo in female adolescents with SSRI-resistant MDD evaluates the significance of treatment-related recovery. In our open-label creatine data, we found that female adolescents with SSRI-resistant MDD showed increased PCr and decreased beta-NTP following creatine augmentation. The effect size of these changes were estimated to be approximately 1.0 (Cohen's d) with 10% SD. Therefore, when we conservatively set the effect size to be 0.9; sample size of 30 per each group; and common SD within a group of 10%, the changes of metabolite levels between creatine and placebo groups will be significantly (alpha level of 0.05) detectable with 86% of power.

ADMINISTRATIVE RESPONSIBILITIES

Resources:

The Brain Institute

The facilities at the University of Utah that are available for the proposed research include the following: the Brain Institute and UNI. The Brain Institute currently occupies 5,900 square feet of office and laboratory space in a building in the University of Utah Research Park adjacent to the Health Sciences campus. It also occupies clinical space in UNI, the site of the Brain Institute's Siemens 3T MRI research scanner.

Recruitment of Participants:

- No “cold calls” will be made by members of the study team.
- An informational flyer will be placed (with permission) on public bulletin boards. The flyer will be submitted to the IRB for approval prior to posting. Examples of public bulletin boards may include but are not limited to: University of Utah bulletin boards (for example, the Health Science Education Building, the College of Nursing, the Department of Psychology, etc.), the Salt Lake Community College, and business frequented by adolescents and their parents.
- An informational brochure has been created, to be displayed (with permission) in appropriate public areas, and to be provided to practicing mental health clinicians, pediatricians and family practitioners in the Salt Lake City area. The clinicians, at their sole discretion and without compensation, will pass the brochure to the parent(s) or guardian(s) of adolescent clients in cases where they deem it appropriate. The brochure will be submitted to the IRB for approval, prior to distribution to clinicians.
- The recruitment flyer and brochure will be posted on the Brain Institute and Department of Psychiatry Internet websites, following approval by the IRB.
- The principal investigator will give presentations to advocacy groups such as NAMI, in which the study is described and parent(s) or guardian(s) are invited to contact the principal investigator to learn more about the study.
- An informational Internet website will be created and submitted to the IRB for approval.
- An IRB-approved paragraph informing University of Utah faculty of the study will be posted in the faculty newsletter (FYI newsletter). The FYI newsletter is published once a month, and we will submit our IRB-approved paragraph to appear in the newsletter up to 12 times per year.

- A webpage describing the study and providing contact information will be uploaded onto the Brain Institute's website at utahbrain.org following IRB approval.
- Study information will be provided to the UNI receiving center to encourage clinician referrals. If a participant calls the Brain Institute regarding study participation and reports that they were referred by a UNI clinician, that clinician will receive a \$5 meal card to the UNI cafeteria.

CONTROL OF INVESTIGATIONAL DRUG

The University of Utah pharmacy's Investigational Drug Service (IDS) will prepare the doses of placebo and 10g of creatine required for the study. IDS will send the study medication in a blinded fashion to the University of Utah Neuropsychiatric Institute (UNI). The study medication will be stored securely at the UNI pharmacy, where it will be stored in a climate-controlled environment and accessible only to pharmacy staff and research personnel. The study will be conducted in compliance with all applicable FDA regulations for IND studies.

The blind will be broken following the culmination of the study or at the request of a medical professional dealing with a medical emergency in a case in which it would help a study participant. IDS will be contacted in order to break the blind.

DATA COLLECTION, MANAGEMENT AND PROTECTED HEALTH INFORMATION

The study team will create case report forms (CRFs) for data collection. The consent, permission and assent forms, CRFs, laboratory results, radiology reports, MRI registration forms, and other necessary documents will be filed in each study participant's binder. Study participant binders will contain protected health information such as name, date of birth, age, address, and phone number. Binders will be stored in locked cabinets located in locked offices. Only essential study team members will have access to participant binders.

Using a password-protected computer with access limited to study personnel, the research team will maintain a computerized screening and enrollment log. Participant screening, eligibility status, and consent for participation status will be recorded in this log. Before the performance of any study procedures, potential participants (and where applicable their parent(s) or guardians(s)), verbal and written informed consent will be obtained. When a participant is screened for study eligibility, they will be assigned a screening ID number. The individual will maintain the screening ID until they have completed the screening visit. If a subject is determined to be ineligible during screening, the reason for the screen failure will be recorded on the computerized screening and enrollment log. Once a subject has completed screening enrolled for study participation, they will be assigned a subject ID number, which will be used to identify all of the data collected from them during the study.

Data from CRFs will be entered into REDCap. REDCap is a secure, web-based application for building and managing online surveys and databases. No personal identifiers from study participants will be entered into REDCap. Forms that have missing or inconsistent data will be recorded in the database; however a "missing data" code will be entered in place of each piece of missing or inconsistent data. Two study team members -- the individual who enters the data, and a second individual monitoring data entry -- will check each CRF form entered into REDCap for accuracy and completeness.

RECORD RETENTION

In keeping with 21CFR312.57, study records will be maintained for at least two years after the drug is approved by the FDA or after shipment and delivery of the drug for investigational use has ceased and the FDA has been notified.

REFERENCES:

